In Phase 1b, we will collect qualitative data in the form of digital recordings (recorded using DVR), transcripts for analysis, and open-ended, paper-and-pencil questionnaires. These interviews will be conducted by a trained RA, with PIs providing comprehensive training and supervision. Interviews will also generate data in the form of written notes, which will contain no individual participant identifiers. We will also collect discussion data directly from participants by asking them to comment and “think aloud” in response to the elements presented to them as they navigate the intervention; these discussions will also be digitally recorded and transcribed. Analyses of these qualitative data will be used to refine the intervention protocol.

In Phase 2, we will collect quantitative data directly from participants using computer-delivered assessments at baseline, 1-month, 3-months, and 6-months. These assessments will produce data on alcohol use and sexual risk behavior during the follow-up periods, and as such, participants will be provided with private spaces within the research offices to complete these measures. All staff members will receive training on ethical follow-up contact and retention strategies. This data will be used as a preliminary evaluation of the intervention on relevant outcomes.

Throughout the study, all procedures and data collection undertaken in face-to-face format will take place in locations that are convenient and private. APRI has arranged for private space to be available for the purposes of conducting the research in both venues. For data collected via computerized assessments, participants will be given privacy to complete these measures. For Phases 1-b and 2, participant contact information will be collected in order to arrange for study sessions, allow contact for any follow-ups, and encourage retention. Confidentiality of participants in these phases will be maintained by assigning them each a unique code number that will be associated with their identifying information in an electronic database that will itself be password-protected and stored on encrypted, secure Brown University servers. Only essential study staff will have access to this file. Participants in Phase 1-c will participate anonymously. Data collected and stored on physical mediums (written notes, digital recordings, written questionnaire data) will be kept in locked file cabinets at Brown University. All personal identifying information collected over the course of the research will be destroyed after the study is completed.

D. RISKS/BENEFITS OF PARTICIPATION

Participation in this study involves no physical risk above those ordinarily encountered in daily life. However, there may be several non-physical risks:

1. There is a small risk of loss of privacy and confidentiality of data, including data that is sensitive (sexual risk-taking, alcohol and drug use, psychological characteristics). We take this risk seriously, and will take steps to protect participants’ confidential data and anonymity, as detailed in Section E. We will ensure that personal identifiers are removed from the data and any publications arising from the study. Informed consent documents will bring confidentiality risks to participants’ attention.
2. Participants may also experience psychological discomfort while completing the intervention procedures and some of the quantitative assessment measures, since

these involve discussion and disclosure of sexual behavior and alcohol/drug use. We will take steps to minimize this discomfort by framing intervention messages as sensitively and non-directively as possible. Research staff will also be trained in a prepared crisis management protocol and have access to additional supervision from [name], who is a licensed psychologist. Research staff will also have lists of referrals to local agencies to address potential psychological problems that may arise in study participants.

D.1. Adequacy of Protection Against Risk

We will make every attempt to minimize risks to participants throughout the study protocol, including loss of privacy or confidentiality and psychological discomfort.

D.1.1. The risk of loss of privacy will be controlled (as described above) by using unique participant ID numbers on all data, rather than participant names. Transcription will be performed by study staff, who will be trained to maintain the confidentiality of interview data by omitting any identifying information when storing data. Only essential staff members will have access to data and research files. Specific forms of data will be protected as follows:

Digital Audio Recordings and Transcripts. Focus groups and interviews in Phases 1a-c will be recorded using digital voice recorders (DVRs). After each day of recording, the Research Assistant will transfer all new recordings from the DVRs to a password-protected computer in a locked project office. They will label files with the number of each focus group (for focus groups) or the Study ID of the individual participant (for participants in the individual interview phase, 1-b). They will listen to the recording in the digital file, and will use audio editing software to edit out any names or identifying information that may appear in the recordings. To store these data, the Research Assistant will then burn these edited files onto a data CD, which will be kept in a locked cabinet in a locked office (which is in a locked suite in a building with a security guard). After burning the voice recording onto these two data CDs, they will delete the original recording from the DVRs. The DVRs will always be kept in the locked cabinet in the RAs office when they contain original recordings. All original recordings will be removed from the recorders before starting a new interview or focus group, and no recording will remain on the DVR for longer than three days. Transcript files will be encrypted and stored securely in a password-protected file, on the password-protected computer in the Contact PI's locked office. Data CDs will be destroyed at the conclusion of the study, once transcription is complete and there is no longer any need for a physical copy of the recording.

Paper-and-pencil Questionnaire Data and Notes. Physical versions of qualitative data collected via handwritten notes taken by research staff and open-ended questionnaire responses (Phases 1a-c) will be labeled with study IDs only, and no identifying information will be recorded. Hard copies of these documents will be stored in locked file cabinets located in Brown University research facilities as long as the study is ongoing, but destroyed upon completion of the research.

Computerized assessment data. Screening data will be collected during Phase 1b, and consist of a small pool of items assessing study inclusion criteria. Quantitative data collected in Phase 2 will be more extensive, and assess screening criteria, responses to items during the intervention, and assessments administered during follow-ups. Screening, intervention-based, and baseline session assessment data will be gathered via online assessments delivered over the tablet. Follow-up assessments will be completed during in-person appointments conducted at the

Brown University research offices. However, all assessments will be delivered via computer, either via Qualtrics® online survey tools (which stores data securely) or via items built-in to the study's custom software. This data will be identified by participants' study IDs only, and will be downloaded weekly and stored in password-protected files on Brown University's servers, which are encrypted. This data will be kept in a separate location from files that link participants' identifying information with their unique study IDs.

Monitoring. The PIs will provide ongoing supervision and training to essential study staff at weekly meetings, which will also ensure continued compliance with data safety protocols. The PIs will also discuss human subjects issues at weekly meetings. Participants in human subjects research inevitably give up some privacy to share data about their individual experiences. However, we believe our data safety and monitoring plan will minimize the risks of any breach of privacy or confidentiality. The PIs will be responsible for ensuring that study protocols for maintaining confidentiality are followed.

Adverse Events. If an Adverse Event is reported, the Contact PI ([name]) will complete an Adverse Events form and report the event to The Brown University IRB and the NIH funding institute within 24 hours. The Contact PI will gather any information needed to investigate the event and to determine subsequent action. The Contact PI will document and report any subsequent action to institutional IRBs and the NIH program officer. DSMBs will also be informed of any adverse events and remedial actions needed. The Contact PI will also generate a brief report of adverse events for the study record each year, and we will forward the report to the institutional IRBs and the NIH funding institute.

D.1.2. The risk of psychological discomfort will be controlled by providing research staff with training on crisis management. [name], a licensed psychologist, will also be available to provide supervision. We will also identify MSM-friendly professional clinical and counseling services that can provide urgent services if needed, and will establish a Memorandum of Understanding with these agencies. During the informed consent process, we will clearly describe the nature of the intervention to participants, which includes discussion of alcohol/drug use and sexual behavior. We will closely monitor any indication of adverse events that might arise from participation in the intervention, and will respond promptly and appropriately by notifying the Brown University IRB.

D2. Potential Benefits

There are no direct benefits to study participants in Phase 1; possible indirect benefits for participants include learning about HIV prevention, testing, and treatment, and having opportunities to discuss their experiences and feelings regarding HIV prevention with investigators. In Phase 2, direct benefits may include opportunities to reflect on HIV risk and drinking behavior with the intervention and receive linkage to further preventive care. However, the MSM community as a whole will likely benefit from the development of the first brief tools for reducing heavy drinking and sex risk. We have instituted multiple procedures to minimize the risks associated with the loss of confidentiality and any discomfort during the study processes. These risks substantially outweigh the potential benefits of the proposed research.

The study will fill critical gaps in the research on interventions for reducing sex risks and related risk factors (heavy drinking) for MSM by providing the first, brief intervention that is

adapted for use in community-based settings. As such, our study will provide important insight into the feasibility and appropriateness of behavior change interventions delivered via tablet in MSM. To our knowledge, no known studies have tested a brief, combined heavy drinking and sex risk reduction intervention in MSM, nor has any published study described the potential for delivering these interventions in a technology-assisted format that can be delivered outside of healthcare settings. As such, this research will result in the development of the first highly disseminable and scalable tool for reducing heavy drinking and sex risk in high-risk MSM.

E. Informed Consent

The informed consent process will be conducted by trained staff members that possess research experience working with the target populations and who are also trained in the ethical treatment of human subjects. Staff members will also be trained in more advanced research topics, such as protocol adherence, quality assurance, data management, and so on. The process of informed consent involves presenting a detailed verbal description of the study as it is described on the printed, IRB-approved consent forms (Appendices C & D). Staff will emphasize that participation is voluntary, and that participants can refuse to answer any question and/or can discontinue participation at any time without penalty. Interviewers will ask whether participants have experienced any coercion to take part in the study; those that describe any pressure or coercion to participate will be excluded. Potential subjects receive an item-by-item reading of the consent form by the study interviewer. Participants will be informed of the procedures for ensuring their confidentiality, including: the use of unique non-personally identifying ID numbers instead of names on research materials, and maintenance of data in locked computer databases and in locked filing cabinets in locked rooms. Compensation for participation will be explained. All participants will be given the contact numbers of the Principal Investigators and IRB Chairs to answer questions about the study or one's rights as a human subject as well as a research site contact number. All consenting participants will be offered a copy of the informed consent form.

Appendices

| Appendix | Content |
|-----------------|--|
| A | Feature Set and Wireframes for Experimental Intervention Content |
| B | Attention Matched Control Content |
| C | Informed Consent Document (Individual Interview participants) |
| D | Informed Consent Document (Pilot study participants) |
| E | Study Measures |
| F | Follow-up Resources Info Card |
| G | Protocol Checklist & Submission Procedures |

References

- ¹Centers for Disease Control and Prevention. (2012). *Estimated HIV incidence in the United States, 2007-2010* (Retrieved from: <http://www.cdc.gov/hiv/topics/surveillance/resources/reports/#supplemental>). Atlanta, GA: U.S. Department of Health and Human Services.

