BI for sex risk reduction. Brief BIs for reducing HIV-risk behavior based on principles of MI focus on exploring current behavior and its consequences, and examining whether this behavior is congruent with one's goals. Based upon these goals, the intervention then provides a menu of options available for behavior change, and discusses various ways of initiating that change and reducing harm based on personal goals. PCC^{9; 10}, one of the only brief BIs for reducing HIV-risk among MSM to date, involves exploring the motivational, interpersonal, and behavioral precursors and effects of a specific unsafe sex episode, and whether these factors contribute to behaviors that are commensurate with one's goals. To facilitate this, PCC uses a questionnaire to guide later education, feedback, and risk reduction planning tailored specifically to participant responses, and thus is highly algorithm-based. As such, elements of PCC are highly amenable to computerization, while achieving optimal relevance to individual participants (see 3C.6. Pilot Data, for more detail about our preliminary adaptation of PCC components). Rather than incorporating all components of PCC (which may result in an overly long intervention), we will incorporate those aspects of PCC that are most consistent with an MI-focus, using these components to support participants' identification/monitoring of factors that contribute to behavior that is discrepant with their goals.

In addition to content related to reducing sex risk behavior, the intervention will also be well-positioned for facilitating patrons' connection with other existing prevention resources (e.g., PrEP, STI screening, further testing). As such, based on the respondents' individual risk profile and previous engagement with these services, additional information will be provided concerning how and where specific resources can be located (see Appendix F for info card).

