BI for alcohol use. Personalized feedback interventions (PFIs) involve delivering feedback on a range of data including comparisons of one's drinking with that of relevant proximal norms, challenging personally-relevant alcohol-related expectancies, conducting decisional balances related to use, presentation of practical use consequences (e.g., time and money spent, calories consumed), as well as strategies for harm reduction⁴⁷. PFIs are frequently delivered electronically and used in conjunction with motivational interviewing (MI)⁴⁸. These interventions can be readily tailored to MSM-specific needs and integrated with sex risk reduction components in an MI-consistent manner. [name] clinical trial with HIV-infected MSM uses this approach.

Combined BI. The proposed combined BI would utilize aspects of existing evidence-based BIs for alcohol use and HIV-risk behavior, and integrate their components to discuss the relationships between the two behaviors, including how engaging in alcohol use can potentiate HIV-risk behavior and how beliefs and attitudes about alcohol can affect this relationship. Combined BIs can also address how one’s goals (e.g., health) and change efforts can be relevant to both behaviors. Table 1 presents an initial, brief outline of possible intervention components. The intervention will first involve a brief assessment completed via tablet, which will ask briefly about sex risk behavior, motivation for reduce drinking and sexual risk (including “stage of change”), collect a 30-day Timeline Follow-Back⁹¹ of alcohol use and sexual behavior, and ask about engagement with other biomedical prevention activities (e.g., PrEP, STI screening). These items will be used to both determine eligibility and inform the content of the intervention. Although the intervention components are separated into discrete topic areas (alcohol use vs. HIV-risk), each component provides an opportunity to present content about how these behaviors intersect. For example, the expectancies module can address alcohol-related sex expectancies, which may promote both drinking and sex risk among MSM²⁹. See Appendix A for additional detail. This process of development will result in a single-session BI, lasting approximately 50 minutes (based on our initial timing of several components; see 3C.3).

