Phase 1c: Theatre testing of BI alpha-version. We will recruit a sample of 10 MSM, using the eligibility criteria from Phase 1b, to conduct a “theatre test” of the BI. MSM who participated in earlier phases will be excluded to provide different perspectives. Participants who are seeking HIV testing at the target venues will be recruited using a screening item concerning their interest in the study that will be included on the standard post-test assessment, and their participation will be anonymous. Interested participants will simply wait in the testing room for study staff after VCT is complete. Staff will then provide them with a tablet and headphones in order to complete the full intervention. Afterward, participants will complete a brief questionnaire and interview about their perceptions of the acceptability and feasibility of delivering a BI in this environment, as well as comments they have about each BI component. Participants will receive \$30 for completing the theatre test.

Qualitative analysis. Recordings of all focus groups and interviews will be transcribed via commercially available software. Data will be analyzed using modified grounded theory methods⁹⁰, with two independent coders arriving at a consensus on major themes identified. This qualitative data will allow us to refine the assessment instruments and BI components for population sensitivity. As such, the study team will review the analysis, and assess the strengths/weaknesses of each of the components based on these findings.

C.4.2. PHASE 2: PILOT TESTING

Specific Aim 2 is to conduct a pilot randomized controlled trial of our BI, and explore preliminary evidence of its efficacy for reducing sexual risk and alcohol use among a sample of high-risk MSM seeking HIV testing in community venues. As such, we will randomize 40 MSM who receive HIV testing at the identified venues to either the standard VCT group + attention-matched control (AC), or the VCT + Intervention (BI) group. We will test the hypothesis that those in the BI group will report reductions in sex risk outcomes, sex under the influence of alcohol, and alcohol use at 1-, 3-, and 6-month follow-ups compared to the VCT+AC group.

C.4.2.1. Methods

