Baseline/Eligibility Assessments. The SDS¹⁷ will be used to assess symptoms of substance dependence for methamphetamine, cocaine, heroin/opiates, and alcohol. The SDS has demonstrated good validity and excellent reliability with respect to these drugs ($\alpha=0.80-0.85$)^{14; 15; 17}. In addition, a 30-day Timeline Follow Back (TLFB)^{18; 19}, administered online, will be used to assess alcohol use and sexual behavior during that period. The TLFB presents a calendar of each recall period, and participants respond by clicking on a box that represents a given day, answering several questions about that day. Questions will assess the number of standard drinks consumed on that day, the number of hours over which these drinks were consumed, the total number of sex partners, their relationship with each (e.g., steady vs. casual), the HIV status of each (e.g., HIV+, HIV-, or unknown), whether they asked about their partner’s HIV/STI status or the last time they were tested, sex acts performed with each, condom use for each act, and whether sexual activity took place while under the influence of alcohol. Meta-analyses have shown that TLFBs for assessing alcohol use and sex behavior are reliable when administered electronically and online²⁰. Other studies explicitly comparing online vs. in-person TLFBs for sexual behavior²¹, and comparing the TLFB to biological measures for alcohol use²² have confirmed the validity of online TLFBs. TLFB data will be used to determine participants’ drinking eligibility, while single items will assess all other eligibility criteria. Finally, stages of change will be assessed using the Stages of Change (Short Form)²³ and a 4-item stages of change measure for HIV-risk²⁴⁻²⁶.

Efficacy outcomes. Our primary outcomes will be the number of unprotected anal sex events, number of sex events under the influence of alcohol, frequency of drinking, and the

number of heavy drinking days over the past month. Outcomes will be assessed via 30-day Timeline Follow Back (TLFB)^{91, 93} at each follow-up.

Secondary outcomes. We will also assess whether participants talked to their partners about their HIV/STI status and recent testing, and whether during each follow-up window, participants engaged in self-initiated HIV testing, sought STI screening, or sought information about pre-exposure prophylaxis. Change motivation and stages will also be explored as secondary outcomes.

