Primary analyses. Our hypotheses related to Specific Aim 2 are that participants in the intervention group will report (1) fewer unprotected anal sex events, (2) fewer events involving sex while under the influence of alcohol, and (3) lower frequency of drinking and a reduced number of heavy drinking days versus the control group. These hypotheses will be evaluated using an intention-to-treat comparison of the rates of our primary outcomes at 1-, 3-, and 6-month follow-ups, using an incidence rate ratio (IRR) and 95% CI. Given the count nature of the data, we will use a Poisson regression covarying for key baseline covariates, and compare IRRs across the two treatment conditions at each time point. As conclusions about statistical significance will be limited due to the small sample, clinically meaningful differences in the pattern of IRRs and means (for alcohol use variables) across groups will be used to evaluate our hypotheses. However, if available data produce stable results, generalized estimating equations (GEEs) using binomial distributions and logit-link functions will also be used to explore differences in these outcomes across time and treatment condition. We will also explore the potential influence of the intervention on secondary outcomes and exploratory mediators. IRRs and descriptive data will be used to compare the groups in terms of their frequency of talking to partners about their status, whether they sought additional HIV testing, STI screening or information about PrEP. Descriptive mean comparisons and linear regressions controlling for baseline values will be used to compare whether HIV knowledge and perceived risk, peer safe sex norms, and safe sex behavioral skills differ across the groups.

C.4.3. Recruitment

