## **STATISTICAL ANALYSIS PLAN**

**Title:** Brief Electronic Intervention for Heavy Drinking and Sex Risk Among Men who have sex with Men  
Seeking HIV Testing

**NCT#:** NCT03435783

**Date of document:** Last reviewed and approved by Brown IRB on 7/21/17

**Statistical analysis plan.** We hypothesized that participants using the web-based intervention would report (1) fewer new anal sex partners, (2) fewer condomless anal sex events, and (3) lower frequency of drinking, (4) lower frequency of binge drinking, and (5) a lower average number of drinks per drinking day versus the control group. These hypotheses will be evaluated using an intention-to-treat comparison of the rates of our primary outcomes at 1-, 2-, and 3-month follow-ups, using incidence rate ratios (IRRs) and 95% CI. Given the count nature of much of the data, we will use a Poisson regression covarying for key baseline covariates, and compare IRRs across the two treatment conditions at each time point. As conclusions about statistical significance will be limited due to the small sample, clinically meaningful differences in the pattern of IRRs and means (for alcohol use variables) across groups will be used to evaluate our hypotheses. However, if available data produce stable results, generalized estimating equations (GEEs) using binomial distributions and logit-link functions will also be used to explore differences in these outcomes across time and treatment condition. We will also explore the potential influence of the intervention on secondary outcomes and exploratory mediators. IRRs and descriptive data will be used to compare the groups in terms of their frequency of talking to partners about their status, whether they sought additional HIV testing, STI screening or information about PrEP. Descriptive mean comparisons and linear regressions controlling for baseline values will be used to compare whether HIV knowledge and perceived risk, peer safe sex norms, and safe sex behavioral skills differ across the groups.

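### The comparisons of STI screening and PrEP-information seeking ignore baseline engagement with those services, although the plan collects it

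*Protocol*

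**What the plan says.** Protocol C.4.1 (BI for sex risk reduction) says that the app also points men to services such as PrEP and STI screening, and that what it gives depends on a man's risk profile and "previous engagement with these services, additional information will be provided concerning how and where specific resources can be located". C.4.1 (Combined BI) says that the opening tablet assessment will "ask about engagement with other biomedical prevention activities (e.g., PrEP, STI screening"; the items in that assessment serve both eligibility and tailoring.

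The outcomes are secondary. C.4.2.2 Measures asks "whether during each follow-up window, participants engaged in self-initiated HIV testing, sought STI screening, or sought information about pre-exposure prophylaxis". For the analysis, the Data Analysis Plan states that "IRRs and descriptive data will be used to compare the groups in terms of their frequency of talking to partners about their status", and the sentence goes on to "whether they sought additional HIV testing, STI screening or information about PrEP". The SAP repeats it. Neither document adds an adjustment, a stratification or a table by prior engagement for these outcomes.

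The same paragraphs do use baseline information elsewhere. For the primary outcomes, "we will use a Poisson regression covarying for key baseline covariates". For the mediators, "Descriptive mean comparisons and linear regressions controlling for baseline values will be used to compare whether HIV knowledge and perceived risk".

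No eligibility list (C.2, C.4.2.1, C.4.4) excludes men who already use PrEP or STI screening. On size, "we will randomize 40 MSM who receive HIV testing at the identified venues". The software assigns the arms, and no stratification is stated.

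**The concern.** Whether a man already uses a service probably predicts whether he reports seeking it during follow-up. A regular screener is likely to say yes in either arm. A man already on PrEP may have little reason to look for information about it. A strong predictor left out of a comparison of about 20 men per arm has two costs: the estimate is less precise than it need be, and a chance surplus of prior users in one arm passes straight into the ratio.

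There is a third, conditional cost. If prior users respond less to the linkage content, the all-men ratio averages over them, and nothing in the plan would show a larger effect in men not yet engaged. This matters because the service outcomes are to be read from the size of the IRRs and from descriptive data, and because the pilot is meant to guide changes before a larger trial.

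**Working it through.** The plan has no power calculation or expected rate for these outcomes, so there is no figure to reproduce. N = 40 is from the protocol. Equal arms of 20 are assumed, and loss to follow-up is ignored. Every rate below is an assumption, chosen to show the mechanism.

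**1. Precision.** Assume 40% already engaged with STI screening, of whom 80% are screened in either arm. Among the others, assume 30% (control) and 45% (intervention).
- Control, all men: 0.4×0.80 + 0.6×0.30 = 0.50; variance 0.50×0.50 = 0.250. Within strata: 0.4×0.16 + 0.6×0.21 = 0.190, which is 24% lower.
- Intervention, all men: 0.4×0.80 + 0.6×0.45 = 0.59; variance 0.59×0.41 = 0.242. Within strata: 0.4×0.16 + 0.6×0.2475 = 0.2125, which is 12% lower.
- Standard error of the risk difference, with strata evenly split between arms: √((0.250+0.242)/20) = 15.7 points unstratified, √((0.190+0.2125)/20) = 14.2 points stratified. The expected difference is 9 points, so this is a gain but not a rescue.

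**2. Chance imbalance.** Take the prior users in each arm as independent Binomial(20, q) counts. The probability that the arms differ by four or more men (20 points) is 6%, 20% and 27% at q = 10%, 25% and 50%.
- Suppose there is no true effect, non-users have a rate of 20% and prior users 80%, and the arms hold 7 and 3 prior users (35% v 15%).
- Crude ratio: (7×0.8 + 13×0.2)/(3×0.8 + 17×0.2) = 8.2/5.8 = 1.41.
- Mantel-Haenszel ratio: (5.6×3/10 + 2.6×17/30)/(2.4×7/10 + 3.4×13/30) = 3.153/3.153 = 1.00.
- With prior-user rates of 5%, 50% and 95%, the crude ratio would be 0.83, 1.24 and 1.48. The error can go either way.

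**3. Masking, only if prior users do not respond.** The all-men rate in each arm is q×(prior-user rate) + (1−q)×(non-user rate).
- STI inputs as in step 1: 0.45/0.30 = 1.50 in non-users, 0.59/0.50 = 1.18 in all men.
- PrEP information, assuming 25% prior users of whom 50% say yes in either arm, others 15% v 30%: 2.0 in non-users, 0.350/0.2375 = 1.47 in all men.
- Wider range, non-users 20% v 50% (ratio 2.5) and prior-user rates from 5% to 95%: 1.98–2.46, 1.58–2.38 and 1.26–2.20 in all men at q = 10%, 25% and 50%.

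**4. What each remedy does.** With strata evenly split, the Mantel-Haenszel ratio equals the crude one. On the STI inputs (8 engaged and 12 not, per arm) both are (6.4+5.4)/(6.4+3.6) = 1.18. Adjustment therefore deals with steps 1 and 2. Only a table by baseline engagement shows step 3.

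**5. Limits.** On the PrEP inputs, the delta-method 95% interval is about 0.55 to 4.0 around 1.47 in all men, and about 0.48 to 8.4 around 2.0 in the 15 non-users per arm. Neither supports a conclusion alone.

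**The case against.** The strongest reply is that nothing is wrong with the planned comparison. The outcomes are defined for all participants, not as first-time linkage. Every participant has just been tested for HIV and the plan still counts further testing, so repeat use is part of the outcome by design. The effect in the whole mix of randomised men is a legitimate question. Chance imbalance is already covered by an ordinary confidence interval. These are exploratory outcomes in a 40-man pilot that itself limits claims of significance. All of this stands, and it is why the all-men comparison should stay the main one. It does not answer the point about precision, and a descriptive ratio read for its size gets no correction when an imbalance actually occurs.

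It might also be said that the IRRs for these outcomes will come from the covariate-adjusted Poisson model. The text attaches that model to the primary outcomes and names no covariates, so even on this reading baseline engagement is not specified.

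Three stronger readings are tempting, and the documents do not support them.
- A reader might infer that men already engaged get little or no resource content, so that dilution is certain. The protocol says only that content depends on engagement, not how it differs. STI screening is repeatable, so a regular screener may still respond.
- A reader might infer that tailoring unbalances the arms. Engagement precedes randomisation, so only chance can do that.
- A reader might conclude that the PrEP comparison should be confined to men not yet engaged. That changes the question and shrinks the sample. If prior users always answered no, it would gain almost nothing: expected z is 0.98 v 0.96 with 20% prior users, and 0.92 v 0.88 with 30%.

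**Conclusion.** The point holds as a missed and almost free improvement, not as a bias. The plan collects baseline engagement and tailors on it but leaves it out of the two comparisons where it is most likely to matter. On the assumed STI rates, stratifying cuts the standard error from 15.7 to 14.2 points. At 25% prior users, about one randomisation in five would carry an imbalance of four or more men, which in the worked null example turns a ratio of 1.00 into 1.41. Masking of a larger effect in men not yet engaged is possible (1.50 seen as 1.18, or 2.0 as 1.47), but only if prior users respond less.

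The size rests on equal arms of 20, on an assumed share of prior users, on prior engagement being prognostic and, for masking, on no response in prior users. The documents give none of these. Both analyses remain far from adequately powered, so the consequence is for how the pilot's ratios are read.

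**What to change.** In the Data Analysis Plan and the SAP:
- Keep the all-randomised comparison as the main one for each service outcome.
- Prespecify that it is stratified by, or adjusted for, baseline engagement with that service, for example with a Mantel-Haenszel ratio.
- Tabulate results by arm and baseline engagement. Include PrEP-information seeking in men not engaged with PrEP at baseline, labelled as supportive.
- Confirm that the item is recorded before randomisation in both arms. Its use for eligibility suggests so, but the baseline battery in C.4.2.2 Measures does not list it.
- Define the strata from the item as asked. The protocol describes engagement, which may not be the same as current PrEP use.

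These outcomes are assessed per follow-up window, and the protocol (1, 3 and 6 months) and the SAP (1, 2 and 3 months) disagree on the windows. The two must be reconciled before the wording is final.

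The cost is a few sentences, provided that the item is collected in both arms. The downside is that small strata give unstable estimates: the supportive PrEP table would hold about 15 men per arm at an assumed 25% prior users. It should be read descriptively.
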